## 4.2 Scientific Rationale for Study Design

### 4.2.1 Rationale for Endpoints

CCI

#### 4.2.1.2 Safety Endpoints

The primary safety endpoint is the incidence of DLTs and number of discontinuations of study treatment due to an AE. Safety and tolerability will be assessed by clinical review throughout the trial. The toxicities and grades experienced by participants who have received study treatment, including AEs, SAEs and events of clinical interest (ECIs) will be summarized. Other safety measures evaluated in study include laboratory tests, ECGs, echocardiogram (ECHO)/multigated acquisition (MUGA) scan, vital signs, ECG measurements, physical examinations, and eye examination.

[figure not shown]
#### 4.2.1.3 Pharmacokinetic Endpoints

Pharmacokinetic endpoint is secondary CCI for selumetinib CCI. CCI Pharmacokinetic profile of selumetinib and pembrolizumab will be characterized. The PK concentrations of selumetinib (and its metabolites) CCI CCI will be used to derive PK parameters of the agents. Furthermore, the results of these analyses will be potentially used in conjunction with the pharmacodynamics, safety, and exploratory endpoint data to help assess future dosing strategies for selumetinib.

CCI

#### **4.2.1.5 Future Biomedical Research**

The Sponsor will conduct future biomedical research on specimens for which consent was provided during this study. This research may include genetic analyses (DNA), gene expression profiling (ribonucleic acid [RNA]), proteomics, metabolomics (serum, plasma), and/or the measurement of other analytes, depending on which specimens are consented for future biomedical research.

Such research is for biomarker testing to address emergent questions not described elsewhere in the protocol (as part of the main study) and will only be conducted on specimens from appropriately consented participants. The objective of collecting/retaining specimens for future biomedical research is to explore and identify biomarkers that inform the scientific understanding of diseases and/or their therapeutic treatments. The overarching goal is to use such information to develop safer, more effective drugs/vaccines, and/or to ensure that participants receive the correct dose of the correct drug/vaccine at the correct time. The details of this future biomedical research substudy are presented in Appendix 6.

#### **4.2.2 Rationale for the Use of Comparator/Placebo**

This study does not include comparators or placebo.

### **4.3 Justification for Dose**

#### **4.3.1 Starting Dose for This Study**

##### **4.3.1.1 Rationale for Starting and Maximum Dose of Selumetinib**

The RP2D for selumetinib as monotherapy is 75 mg PO BID, administered continuously. In this study, the starting dose of selumetinib will be 50 mg oral BID dosed intermittently for the first 14 days of each 21-day cycle. The dose will be escalated, in 25-mg increments, to above 200 mg (up to 300 mg) oral BID per the mTPI rule, maintaining the intermittent schedule. Outcomes of phase II trial of selumetinib propose that enhanced inhibition of MEK

is associated with a greater clinical response, but MEK inhibition also causes dose dependent AEs. Thus, intermittent dosing might have better results than continuous administration. Preclinical studies have demonstrated that intermittent dosing may delay the development of acquired resistance [Faghfuri, E., et al 2018] [Xue, Y., et al 2017].

#### 4.3.1.2 Rationale for Dose Interval and Escalation Increments

Doses of selumetinib will start at 50 mg BID, below the monotherapy RP2D dose for selumetinib of 75 mg BID. Dose escalation increments for selumetinib in combination with pembrolizumab will be to 75 mg (50% increase) initially, to the monotherapy RP2D for selumetinib, and then 33% or lower afterwards in increments of 25 mg.

- Starting Dose (Dose Level [DL] 1): MK-5618 50 mg (oral) twice daily (BID), 2 weeks on/1 week off + MK-3475 200 mg IV every 3 weeks (Q3W)
- Escalation Dose (DL2): MK-5618 75 mg (oral) BID, 2 weeks on/1 week off + MK-3475 200 mg IV Q3W
- Escalation Dose (DL3): MK-5618 100 mg (oral) BID, 2 weeks on/1 week off + MK-3475 200 mg IV Q3W
- Escalation Dose (DL4): MK-5618 125 mg (oral) BID, 2 weeks on/1 week off + MK-3475 200 mg IV Q3W
- Escalation Dose (DL5): MK-5618 150 mg (oral) BID, 2 weeks on/1 week off + MK-3475 200 mg IV Q3W
- Escalation Dose (DL6): MK-5618 200 mg (oral) BID, 2 weeks on/1 week off + MK-3475 200 mg IV Q3W
- Escalation Dose (DL7 onwards): MK-5618 above 200 mg (up to 300 mg; oral) BID, 2 weeks on/1 week off + MK-3475 200 mg IV Q3W

This Dose Escalation study will follow the mTPI method (Section 4.3.1.4) to identify the preliminary RP2D of selumetinib used in combination with pembrolizumab.

#### 4.3.1.3 Rationale for Fixed Dose Pembrolizumab

The planned dose of pembrolizumab for this study is 200 mg every 3 weeks (Q3W). Based on the totality of data generated in the Keytruda development program, 200 mg Q3W is the appropriate dose of pembrolizumab for adults across all indications and regardless of tumor type. As outlined below, this dose is justified by:

- Clinical data from 8 randomized studies demonstrating flat dose- and exposure-efficacy relationships from 2 mg/kg Q3W to 10 mg/kg every 2 weeks (Q2W),

- Clinical data showing meaningful improvement in benefit-risk including overall survival at 200 mg Q3W across multiple indications, and
- Pharmacology data showing full target saturation in both systemic circulation (inferred from PK data) and tumor (inferred from physiologically-based PK analysis) at 200 mg Q3W.

Among the 8 randomized dose-comparison studies, a total of 2262 participants were enrolled with melanoma and NSCLC, covering different disease settings (treatment naïve, previously treated, PD-L1 enriched, and all-comers) and different treatment settings (monotherapy and in combination with chemotherapy). Five studies compared 2 mg/kg Q3W versus 10 mg/kg Q2W (KN001 Cohort B2, KN001 Cohort D, KN002, KN010, and KN021), and 3 studies compared 10 mg/kg Q3W versus 10 mg/kg Q2W (KN001 Cohort B3, KN001 Cohort F2 and KN006). These studies demonstrated flat dose- and exposure-response relationships across the doses studied representing an approximate 5- to 7.5-fold difference in exposure. The 2 mg/kg (or 200 mg fixed-dose) Q3W provided similar responses to the highest doses studied. Subsequently, flat dose-exposure-response relationships were also observed in other tumor types including head and neck cancer, bladder cancer, gastric cancer and classical Hodgkin Lymphoma, confirming 200 mg Q3W as the appropriate dose independent of the tumor type. These findings are consistent with the mechanism of action of pembrolizumab, which acts by interaction with immune cells, and not via direct binding to cancer cells.

Additionally, pharmacology data clearly show target saturation at 200 mg Q3W. First, PK data in KN001 evaluating target-mediated drug disposition conclusively demonstrated saturation of PD-1 in systemic circulation at doses much lower than 200 mg Q3W. Second, a physiologically-based PK analysis was conducted to predict tumor PD-1 saturation over a wide range of tumor penetration and PD-1 expression. This evaluation concluded that pembrolizumab at 200 mg Q3W achieves full PD-1 saturation in both blood and tumor.

Finally, population PK analysis of pembrolizumab, which characterized the influence of body weight and other participant covariates on exposure, has shown that the fixed-dosing provides similar control of PK variability as weight-based dosing, with considerable overlap in the distribution of exposures from the 200 mg Q3W fixed dose and 2 mg/kg Q3W dose. Supported by these PK characteristics, and given that fixed-dose has advantages of reduced dosing complexity and reduced potential of dosing errors, the 200 mg Q3W fixed-dose was selected for evaluation across all pembrolizumab protocols.

#### **4.3.1.4 Dose Finding Using a Modified Toxicity Probability Interval Design**

Dose finding will follow the mTPI design [Ji Y, Li Y, Bekele BN 2007] with a target DLT rate of 30%. Dose escalation and de-escalation decisions are based on the mTPI design and depend on the number of participants enrolled and number of DLTs (Section 6.6.2.2) observed at the current dose level. The DLT observation period for this trial is defined as 21 days for the participant.

A minimum of 3 participants are required at each dose. However, depending on the accrual rate, 3, 4, 5, or 6 participants may be enrolled within 7 to 14 days of initiating the current

dose level. In [Table 1](#), the columns indicate the numbers of participants treated at the current dose level, and the rows indicate the numbers of participants experiencing DLT. The entries of the table are the dose-finding decisions: E, S, D, and DU represent escalating the dose, staying at the same dose, de-escalating the dose, and excluding the dose from the trial due to unacceptable toxicity, respectively. For example, if 0 out of 3 participants at a given dose level develop a DLT, then the dose can escalate to the next level. If 2 participants out of 3 develop a DLT, the dose will be de-escalated to the next lower dose level. If 3 out of 3 participants develop a DLT, this indicates an unacceptable toxicity at this dose. The dose should be de-escalated and the current dose will not be explored further. If 1 out of 3 participants at a given dose level develops a DLT, then additional participants should be enrolled at that dose level following the rules below.

When adding participants to a dose level in response to a “stay” decision, the number of additional participants to be enrolled is capped to minimize the exposure to a dose that may be unacceptably toxic (denoted as DU in [Table 1](#)). Secondly, to determine how many more participants can be enrolled at the dose level, one can count steps in diagonal direction (down and to the right) from the current cell to the first cell marked DU. For example, if 1 of 3 participants have experienced a DLT at a given dose level, no more than an additional 3 participants should be enrolled at this dose level until additional DLT data are available. This is because this dose level would be considered unacceptably toxic if all 3 of the additional participants experience a DLT (ie, 4/6 participants with DLT in [Table 1](#)). The same principles will be applied whether 3, 4, 5, or 6 participants are initially enrolled at that dose level.

A D or DU decision at the lowest dose level will stop the trial. An E decision at the highest dose level will result in staying at that level.

Dose finding will end after 14 participants have been enrolled at any of the tested doses and the decision is to stay at the current dose. After 14 participants have been enrolled at any of the tested doses, dose finding will stop if the mTPI table indicates “S” for staying at current dose. Otherwise, up to 14 new participants may be enrolled at a lower dose if “D” or “DU” is indicated, or at a higher dose if “E” is indicated.

The pool-adjacent-violators-algorithm [Ji, Y. 2013] will be used to estimate the DLT rates across doses. The dose with an estimated DLT rate closest to 30% will be treated as a preliminary MTD. However, the totality of the data will be considered before deciding on the dose(s) to carry forward to Part 2, and the escalation schedule may be adjusted based on PD, PK, and safety data emerging throughout the trial.

Note that although 30% was the target toxicity rate used to generate the guidelines in [Table 1](#), the observed rates of participants with DLTs at the MTD may be slightly above or below 30%).

Table 1 Dose-finding Rules per mTPI Design

Number of Participants with at least 1 DLT	Number of Participants Evaluable for DLT at Current Dose											
	3	4	5	6	7	8	9	10	11	12	13	14
0	E	E	E	E	E	E	E	E	E	E	E	E
1	S	S	S	E	E	E	E	E	E	E	E	E
2	D	S	S	S	S	S	S	S	E	E	E	E
3	DU	DU	D	S	S	S	S	S	S	S	S	S
4		DU	DU	DU	D	D	S	S	S	S	S	S
5			DU	DU	DU	DU	DU	D	S	S	S	S
6				DU	DU	DU	DU	DU	DU	D	S	S
7					DU	D						
8						DU						
9							DU	DU	DU	DU	DU	DU
10								DU	DU	DU	DU	DU
11									DU	DU	DU	DU
12										DU	DU	DU
13											DU	DU
14												DU

Abbreviations: D = De-escalate to the next lower dose; DU = The current dose is unacceptably toxic; E = Escalate to the next higher dose; S = Stay at the current dose.

Target toxicity rate = 30%

Flat noninformative prior Beta (1,1) is used as a prior and  $\varepsilon_1=\varepsilon_2=0.03$  [Ji Y, Li Y, Bekele BN 2007] [Ji, Y. 2013] [Ji, Y., et al 2010]

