### Number of Participants:

Approximately 50 participants will be enrolled in this dose escalation study, as described in Section 9; the overall sample size will be 84 participants maximum for this dose escalation study.

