### **9.9 Sample Size and Power Calculations**

With a maximum sample size of 14 at each dose level, the overall sample size for this Phase 1 trial is expected to be approximately 50. The maximum overall sample size is 84. The actual sample size depends on the safety profiles and number of doses studied.

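### The rule for adding participants after a dose reaches 14 does not count those already treated at the neighbouring dose, so it conflicts with the maximum of 14 per dose and runs past Table 1

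*Combined protocol and SAP*

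**What the plan says.** Section 4.3.1.4 sets out dose finding by mTPI with a 30% target. Four of its provisions matter here.

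- Entry at a dose: "A minimum of 3 participants are required at each dose".
- Ending: once a dose has 14 participants, "dose finding will stop if the mTPI table indicates" S.
- Otherwise: "up to 14 new participants may be enrolled at a lower dose" after D or DU. The same allowance applies at a higher dose after E.
- Table 1: the columns are headed "Number of Participants Evaluable for DLT at Current Dose" and run from 3 to 14. Its key sends D to the next lower dose.

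Section 9.9 then describes the sample size with these words: "With a maximum sample size of 14 at each dose level".

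**The concern.** The allowance counts new participants only. That is harmless when the indicated dose is untested, because 0 + 14 = 14. It is not harmless after D or DU, because the next lower dose was treated on the way up. The same holds for an E pointing to a higher dose that was treated earlier and left by a D decision.

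In those cases Sections 4.3.1.4 and 9.9 give different limits for the same dose. If the larger limit is used, the count passes the last column of Table 1 and no tabulated decision is available. This is the enrolment rule of a dose-escalation trial whose primary endpoints include DLTs, so it should have one reading.

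**Working it through.** **Inputs.** From Section 4.3.1.4: at least 3 participants per dose, up to 14 new after a non-S decision at 14, Table 1 columns 3 to 14, target 0.30, Beta(1,1) prior, both epsilons 0.03. From Section 9.9: maximum 14 per dose. The cutoff for DU is not stated. I assumed DU when the posterior probability that the DLT rate exceeds 0.30 is above 0.95.

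**Step 1: reproduce Table 1.** With x DLTs in n, the posterior is Beta(1 + x, 1 + n − x). The decision is the interval with the largest posterior probability per unit length: below 0.27 gives E, 0.27 to 0.33 gives S, above 0.33 gives D. DU overrides. All legible cells in rows 0 to 6 match. At n = 14 the rebuilt column is E for 0 to 2 DLTs, S for 3 to 6, D for 7, DU for 8 or more. The cell 7/14 is close to the assumed DU cutoff (posterior probability 0.94999), but row 7 of the printed table also ends in D.

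**Step 2: how many are already at the next lower dose?** On the way up it was left by an E decision. E cells exist at every n from 3 to 14, so it holds 3 to 14.

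**Step 3: literal ceiling.** Number already there + 14:

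- minimum: 3 + 14 = 17
- maximum: 14 + 14 = 28

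These are upper limits on what the text permits, not expected counts.

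**Step 4: can both ends be reached under the rules?** Section 4.3.1.4 caps additions after S by counting diagonal steps to the first DU cell.

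- *Upper dose to D at 14:* 1/3, 2/6, 3/9 and 5/12 (all S), then 7/14 (D). The diagonal limits at the four S cells are 3, 3, 4 and at least 2. The additions are 3, 3, 3 and 2, so all are allowed.
- *Lower dose at 3:* 0/3 is E. With the path above, the ceiling is 17.
- *Lower dose at 14:* 2/6 (S), 2/9 (S), 2/14 (E). The diagonal limits are 3 and at least 5. The additions are 3 and 5, so both are allowed. With the path above, the ceiling is 28.

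**Step 5: the cumulative reading.** If 14 is a total, the number that may be added is 14 minus those already there: 14 − 3 = 11 in the first example and 14 − 14 = 0 in the second. In the second, the lower dose stands at 2/14 (E) and the next at 7/14 (D). Nobody can be added where the table points, and neither cell is S, so the stated end condition is not met. The same holds with 0/14 or 1/14 below.

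**Step 6: frequency.** The documents give no DLT curves, so this rests on assumptions. With seven levels, cohorts of 3 or 6 and a range of flat and rising curves, D or DU at 14 with a treated dose below occurred in none to about 5% of simulated trials. The figure moves with the curves and with coding choices, so only the order of magnitude should be used.

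**The case against.** **The two sections can be read together.** The allowance is permissive and phrased as an upper limit, while Section 9.9 states a maximum, so the maximum could govern. This is a sensible reading and probably the intended one. But the clause speaks of new participants and nothing in it points to Section 9.9. Step 5 shows that the cumulative reading still leaves a gap.

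**A reader might infer that no decision exists past 14.** That goes too far. The target, prior and epsilons are given, so E, S and D can be computed for any n. Only the DU cutoff is unstated. What holds is that Table 1 tabulates none.

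**The open case is narrow.** This stands. With 8 or more DLTs in 14 the upper dose is excluded. The lower dose is then arguably the highest remaining, and E at the highest dose means staying. Only exactly 7/14 is left open. It may be added that isotonic estimation would still pick a dose. With 2/14 and 7/14 the estimates are 14.3% and 50.0%, and the lower is nearer 30% (15.7 against 20.0 points). With 1/14 below, the estimate is 7.1%, which is 22.9 points away, so the dose just marked D would be nearer. The estimate therefore does not replace a stated end rule.

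**A reader might infer that the overall maximum is also wrong**, since 84 = 6 × 14 while the ladder runs on ("Escalation Dose (DL7 onwards): MK-5618 above 200 mg (up to 300 mg; oral) BID") and 7 × 14 = 98. The documents do not support this. They never derive 84 from a number of levels. The Synopsis states it as a limit in its own right ("the overall sample size will be 84 participants maximum for this dose escalation study"), and Section 9.9 repeats it ("The maximum overall sample size is 84"). No simulated seven-level trial exceeded it.

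**Conclusion.** The inconsistency is real and minor. As written, Section 4.3.1.4 permits up to 17 to 28 participants at a previously treated lower dose. Section 9.9 allows 14, and Table 1 stops at 14. The same defect affects an E toward a higher dose treated earlier. A cumulative reading resolves the count but not the case of 0 to 2 in 14 (E) below exactly 7 in 14 (D).

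The ceiling range is arithmetic on the documents' own figures and needs no assumption. That 7/14 is D rather than DU rests on the rebuilt table with a 0.95 cutoff, in agreement with the last entry of row 7. The statement that the situation is uncommon, a few percent of trials at most, rests on assumed DLT curves. Decisions up to n = 14, the isotonic DLT estimate, the planning size of about 50 and the overall maximum of 84 are not affected.

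**What to change.** Reconcile Sections 4.3.1.4 and 9.9 in two sentences.

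1. Make the per-dose maximum explicitly cumulative, for example: after a non-S decision at 14, additional participants may be enrolled at the indicated dose up to a cumulative total of 14 at that dose.
2. State how dose finding concludes when the indicated neighbouring dose already holds 14, for example by ending enrolment and estimating DLT rates by the planned isotonic regression.

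If the sponsor does intend more than 14 at a dose, Section 9.9 must say so, and Table 1 must be extended to every count allowed.

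The cost of the two-sentence version is very low. Table 1, the 30% target, the estimation method, the planning size and the maximum of 84 stay as they are, and no extra participants are needed.

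### The preliminary-MTD rule is not limited to doses that were not excluded as DU, so read literally it can name a dose the trial has already removed as unacceptably toxic

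*Combined protocol and SAP*

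**What the plan says.** In the combined protocol and SAP, section 4.3.1.4 defines DU as "excluding the dose from the trial due to unacceptable toxicity" and, for 3 DLTs in 3 participants, adds: "The dose should be de-escalated and the current dose will not be explored further".

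Later in the same section, dose finding ends when a dose has 14 participants and Table 1 shows S. For the other cases: "Otherwise, up to 14 new participants may be enrolled at a lower dose if" the table shows D or DU, or at a higher dose if it shows E. There are two boundary rules. D or DU at the lowest level stops the trial, and E at the highest level means staying there.

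DLT rates are then estimated by the pool-adjacent-violators algorithm, and "The dose with an estimated DLT rate closest to 30% will be treated as a preliminary MTD". Section 9.6.2 describes the same fit, weighted by sample size, across doses. Neither place limits the candidates to doses that were not excluded. Section 9.9 sets a maximum of 14 participants per dose level.

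**The concern.** The exclusion appears in the escalation rules and is not repeated in the selection rule. The selection rule looks only at distance from 30%, so an over-toxic dose can win whenever the dose below it is almost free of DLTs. Establishing a preliminary recommended Phase 2 dose is part of the primary objective, and the preliminary MTD is the main statistical input to it. A written rule that can return a dose the safety rule has removed should not depend on the reader to correct it.

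The rule for 14 participants has a related gap. It speaks of a higher dose on E without excepting one that is excluded or already full.

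**Working it through.** **Reproducing Table 1.** Inputs from section 4.3.1.4: target rate 0.30, the prior ("Flat noninformative prior Beta (1,1) is used as a prior and") and half-widths of 0.03. With x DLTs in n participants the posterior is Beta(1+x, 1+n−x). The decision is the largest of P(p<0.27)/0.27 for E, P(0.27<p<0.33)/0.06 for S and P(p>0.33)/0.67 for D. It is replaced by DU if P(p>0.30) exceeds a cutoff. The cutoff is not stated; I assume 0.95. All 78 legible cells (rows 0 to 6) match. The table is consistent with 0.95: 4/7 is D with P(p>0.30) = 0.942, and 5/9 is DU with 0.953.

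**A path that reaches the problem.** At the upper dose, 1/3 is S. The diagonal cap runs 2/4, 3/5, 4/6 (DU), so 3 more may enter. Then 2/6 is S, and the cap runs 3/7, 4/8, 5/9 (DU), so again 3 more. If all three have a DLT, the result is 5/9, DU. The lower dose has no DLTs. Its raw rate is 0 whether it holds 3 or 14 participants, and the two rates are already in order, so nothing is pooled.

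A second path is 1/3, 3/6, 3/8, 6/11, with caps of 3, 2 and 3. Table 1's row for six DLTs reads "DU DU DU DU DU DU D S S" for n = 6 to 14, so 6/11 is DU.

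| Data | Raw rate | Distance from 0.30 | Posterior mean (x+1)/(n+2) | Distance from 0.30 |
|---|---|---|---|---|
| 0/14 | 0 | 0.300 | 1/16 = 0.0625 | 0.2375 |
| 1/14 | 0.071 | 0.229 | 2/16 = 0.125 | 0.175 |
| 5/9 (DU) | 0.556 | 0.256 | 6/11 = 0.5455 | 0.2455 |
| 6/11 (DU) | 0.545 | 0.245 | 7/13 = 0.5385 | 0.2385 |
| 7/13 (DU by formula; row broken in the text) | 0.538 | 0.238 | 8/15 = 0.5333 | 0.2333 |

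With raw rates, all three DU results beat a lower dose with no DLTs, and a single DLT in 14 below reverses each of them. With posterior means, 5/9 and 6/11 lose to 0/14, while 7/13 still wins narrowly. Beta(1,1) is named for Table 1 and for the credible interval in section 9.6.2. It is not named for the isotonic fit.

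**A stop at DL1.** If DL1 is marked DU (for example 3/3) the trial stops with DL1 as the only tested dose. The closest-to-30% sentence then has no other candidate.

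**How often.** The documents give no true toxicity curve, so these are ranges under assumed curves. One simulation used 20,000 trials per scenario, 7 levels, cohorts of up to 3 or up to 6, the diagonal cap and raw-rate pooling. Where E pointed to an excluded or full dose before 14, enrolment was assumed to continue at the current dose.

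| Assumed curves | DU dose named MTD | E at 14 below a DU dose | E at 14 next to D at 14 |
|---|---|---|---|
| Smooth (MTD at DL2, DL4 or DL6) | 0.2–1.5% (DL1 stops included) | 11–18% | 1.1–1.8% |
| Jump between adjacent doses (8→50%, 10→55%, 5→45%) | 4.6–7.4% | 48–63% | 3.9–5.2% |
| DL1 truly 50% | 27–52%, all DL1 stops | about 0.5% | about 0% |

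The highest smooth figure, 1.51%, includes 0.85 points from DL1 stops, which leaves 0.66%. Other runs with different assumed curves gave 0.02–0.6% (smooth) and 1.3–9.8% (jump) for naming a DU dose. They gave 5–18% and 52–82% for E at 14 below a DU dose, and 1–9% for E at 14 next to D at 14. Ties between isotonic estimates occurred in 2–8% of trials on smooth curves and 23–52% on jumps.

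Restricting the choice to doses not marked DU brought the naming of an excluded dose to 0 in every scenario.

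**The case against.** The section can be read as a whole. A dose excluded from the trial is not a natural MTD candidate, and most teams would read it that way. The MTD is only preliminary, the totality of the data decides which dose goes forward, and expansion needs an amendment, so an excluded dose would not be advanced mechanically. The result also depends on raw rates and on toxicity jumps that no document asserts. All of this limits the consequence. It does not supply the missing restriction, the input to the fit or a tie rule.

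Two stronger readings are tempting and are not supported:

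- A reader might infer that the plan directs new participants to an excluded dose when E appears at 14. The wording there is permissive, and the same section says an excluded dose is not explored further.
- A reader might infer that many trials end with no workable rule. The exclusion, together with the maximum of 14 per dose in section 9.9, implies that enrolment ends there, and the MTD sentence can then be applied. In one set of runs, among trials ending at E with 14 below a DU dose (DL1 stops aside), the literal rule chose the dose directly below the DU dose, alone or as the highest of a tied group, in 97–99% on smooth curves and 93–96% on jumps.

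**Conclusion.** The point holds in a limited form. The selection rule and the isotonic estimate do not carry the DU exclusion forward, and a path allowed by Table 1 and its cap leads the literal rule to an excluded dose. With DL1 stops set aside, this happens in under about 1.5% of trials on smooth curves and up to about 10% on steep jumps. Those figures rest on assumed curves, the assumed 0.95 cutoff and raw rates; with posterior means the problem nearly vanishes. A DU stop at DL1 is a separate case, in which the sentence can only return DL1.

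The 14-participant wording is a conflict to reconcile. E at 14 below an excluded dose arises in about 5–20% of trials on smooth curves and about half or more on the assumed jumps. These are rates of meeting unreconciled wording. They are not rates of a wrong or missing MTD.

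**What to change.** In sections 4.3.1.4 and 9.6.2, write: *Among doses tried and not marked DU, the dose with the isotonic estimate closest to 30% is the preliminary MTD; if no such dose remains, no MTD is declared.* Excluded doses stay in the isotonic fit; only the choice is restricted. State whether raw rates or Beta(1,1) posterior means enter the fit, and give one fixed rule for tied estimates.

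Separately, reconcile the exclusion and the 14-participant rule in section 4.3.1.4 with the per-dose maximum in section 9.9, so that the text covers E at 14 when the next dose is excluded, and E at 14 next to a dose that is D at 14. The second case needs its own sentence, because the DU restriction does not reach it.

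The cost is a few sentences, made by protocol amendment as section 9.1 requires for methods tied to the primary objective. No added participants or data are needed.
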